Appendix K

Fugl-Meyer Assessment - Upper Extremity

FMA-UE PROTOCOL

Rehabilitation Medicine, University of Gothenburg

FUGL-MEYER ASSESSMENT
UPPER EXTREMITY (FMA-UE)
Assessment of sensorimotor function

ID:

Date:

Examiner:

A. UPPER EXTREMITY , sitting position		
I. Reflex activity	none	can be elicited
Flexors: biceps and finger flexors (at least one)	0	2
Extensors: triceps	0	2
Subtotal I (max 4)		
II. Volitional movement within synergies, without gravitational help	none	partial
Flexor synergy: Hand from contralateral knee to ipsilateral ear. From extensor synergy (shoulder adduction/ internal rotation, elbow extension, forearm pronation) to flexor synergy (shoulder abduction/ external rotation, elbow flexion, forearm supination).	0	1
Extensor synergy: Hand from ipsilateral ear to the contralateral knee	0	2
Shoulder elevation	0	1
Elbow external rotation	0	1
Forearm flexion	0	1
Forearm supination	0	1
Shoulder adduction/internal rotation	0	1
Elbow extension	0	1
Forearm pronation	0	1
Subtotal II (max 18)		
III. Volitional movement mixing synergies, without compensation	none	partial
Hand to lumbar spine hand on lap	0	1
Shoulder flexion 0°- 90° elbow at 0° pronation-supination 0°	0	1
Pronation-supination elbow at 90° shoulder at 0°	0	1
Subtotal III (max 6)		
IV. Volitional movement with little or no synergy	none	partial
Shoulder abduction 0 - 90° elbow at 0° forearm pronated	0	1
Shoulder flexion 90° - 180° elbow at 0° pronation-supination 0°	0	1
Pronation/supination elbow at 0° shoulder at 30°- 90° flexion	0	1
Subtotal IV (max 6)		
V. Normal reflex activity assessed only if full score of 6 points is achieved in part IV; compare with the unaffected side	0 (IV), hyper	lively
biceps, triceps, finger flexors	2 of 3 reflexes markedly hyperactive or 0 points in part IV 1 reflex markedly hyperactive or at least 2 reflexes lively maximum of 1 reflex lively, none hyperactive	1
Subtotal V (max 2)		
Total A (max 36)		

Approved by Fugl-Meyer AR 2010

1

Updated 2015-03-11

Appendix L

Action Research Arm Test (ARAT)

ACTION RESEARCH ARM TEST

Patient Name: _____
Rater Name: _____
Date: _____

Instructions

There are four subtests: Grasp, Grip, Pinch, Gross Movement. Items in each are ordered so that:

- if the subject passes the first, no more need to be administered and he scores top marks for that subtest;
- if the subject fails the first *and* fails the second, he scores zero, and again no more tests need to be performed in that subtest;
- otherwise he needs to complete all tasks within the subtest

Activity	Score
-----------------	--------------

Grasp

1. Block, wood, 10 cm cube (If score = 3, total = 18 and to Grip)
Pick up a 10 cm block

2. Block, wood, 2.5 cm cube (If score = 0, total = 0 and go to Grip)
Pick up 2.5 cm block

3. Block, wood, 5 cm cube

4. Block, wood, 7.5 cm cube

5. Ball (Cricket), 7.5 cm diameter

6. Stone 10 x 2.5 x 1 cm

Coefficient of reproducibility = 0.98

Coefficient of scalability = 0.94

Grip

1. Pour water from glass to glass (If score = 3, total = 12, and go to Pinch)

2. Tube 2.25 cm (If score = 0, total = 0 and go to Pinch)

3. Tube 1 x 16 cm

4. Washer (3.5 cm diameter) over bolt

Coefficient of reproducibility = 0.99

Coefficient of scalability = 0.98

Pinch

1. Ball bearing, 6 mm, 3rd finger and thumb (If score = 3, total = 18 and go to Grossmt)

2. Marble, 1.5 cm, index finger and thumb (If score = 0, total = 0 and go to Grossmt)

3. Ball bearing 2nd finger and thumb

4. Ball bearing 1st finger and thumb

5. Marble 3rd finger and thumb

6. Marble 2nd finger and thumb

Coefficient of reproducibility = 0.99

Coefficient of scalability = 0.98

Provided by the Internet Stroke Center — www.strokecenter.org

**Grossmt (Gross Movement)**

1. Place hand behind head (If score = 3, total = 9 and finish)

2. (If score = 0, total = 0 and finish)

3. Place hand on top of head

4. Hand to mouth

Coefficient of reproducibility = 0.98

Coefficient of scalability = 0.97

Appendix M
Therapy Follow Up Checklist

**Please answer the following questions regarding therapy visits
that have been received since the last study visit**

Occupational Therapy	YES/NO	# of sessions	Session Length
Therapy addressed:	 Home exercise program  Self-care (dressing, toileting, etc)  Household tasks (cooking, cleaning, etc)  Return to worktasks  Coordination  Community tasks (shopping, using public transportation, etc)  Cognition (memory, multi-tasking, attention, etc)	 Transfers  Casting/splinting  Vision  Sitting/standing balance  Arm/hand exercises - Number of repetitions: _____	
Physical Therapy	YES/NO	# of sessions	Session Length
Therapy addressed:	 Walking  Running  Vestibular exercises  Leg exercises - Number of repetitions: _____	 Rolling in bed  Standing balance  Transfers  Casting/bracing - Number of repetitions: _____	 Sitting balance  Home exercise program  Getting in/out of bed  Core exercises - Number of repetitions: _____
Speech Therapy	YES/NO	# of sessions	Session Length
Therapy addressed:	 Cognition (memory, multi-tasking, attention, etc)  Communication (speaking and/or understanding)  Swallowing		

Appendix N

Home Exercises that the Rehabilitation Therapist will Select for the Stroke Survivor

HEP2GO Home Exercise Program
Created by [name], OTR Apr 15th, 2022

View videos at www.HEP.video

Total 11

SCAPULAR RETRACTIONS
Move your shoulder blades back and down.
Hold, relax and repeat.

[figure not shown]
Repeat 10 Times
Hold 5 Seconds
Complete 2 Sets
Perform 4 Times a Week

AROM SHOULDER ABDUCTION
With your affected arm starting at your side with your thumb pointed upward, raise up your arm to the side.

Repeat 10 Times
Hold 5 Seconds
Complete 2 Sets
Perform 4 Times a Week

Video # VVNFC7TNL

AROM FLEXION
While sitting or standing with your arm at your side, slowly raise it up and forward towards overhead.

Repeat 10 Times
Hold 5 Seconds
Complete 2 Sets
Perform 4 Times a Week

Video # VVBNSZXGV

Total 13

**SHOULDER - ISOMETRIC EXTERNAL ROTATION**

Gently press your hand into a wall using the back side of your hand. Maintain a bent elbow the entire time.

Repeat 10 Times
Hold 5 Seconds
Complete 2 Sets
Perform 4 Times a Week

**SHOULDER - ISOMETRIC FLEXION**

Gently push your fist forward into a wall with your elbow bent.

Repeat 10 Times
Hold 5 Seconds
Complete 2 Sets
Perform 4 Times a Week

**SHOULDER - ISOMETRIC ABDUCTION**

Gently push your elbow out to the side into a wall with your elbow bent.

Repeat 10 Times
Hold 5 Seconds
Complete 2 Sets
Perform 4 Times a Week

**ELASTIC BAND FLEXION - SELF FIXATION**

While holding an elastic band in front of you and on your leg with your unaffected arm, pull the band upward towards the ceiling with your affected arm as shown.

Video # VVVRN4D7C

Repeat 10 Times
Complete 2 Sets
Perform 4 Times a Week

**ELASTIC BAND SHOULDER DIAGONAL - FLEXION ABDUCTION - SELF FIX**

Start by holding an elastic band down by your side to fixate it with your unininvolved arm. Next, using the involved arm, draw the other end of the band upwards and towards the opposite side as shown.

Video # VV7BGW6RU

Repeat 10 Times
Complete 2 Sets
Perform 4 Times a Week

**ELASTIC BAND BILATERAL EXTERNAL ROTATION - ER**

While holding an elastic band with your elbows bent, pull your hands away from your stomach area. Keep your elbows near the side of your body.

Video # VVEL2H3YQ

Repeat 10 Times
Complete 2 Sets
Perform 4 Times a Week

Appendix O

11. **What is the primary purpose of the *Journal of Clinical Endocrinology and Metabolism*?**

For more information, contact the Office of the Vice President for Research and Economic Development at [contact] or [contact].

For more information, contact the Office of the Vice President for Research and the Office of the Vice President for Student Affairs.

© 2024 All rights reserved. This material may not be reproduced without the express written consent of the author.

11. **What is the primary purpose of the *Journal of Clinical Endocrinology and Metabolism*?**

Black box

[REDACTED]

© 2013 by the author; licensee MDPI, Basel, Switzerland. This article is an open access article distributed under the terms and conditions of the Creative Commons Attribution license (<http://creativecommons.org/licenses/by/3.0/>).

1000

Appendix P
Proposed Study Timeline December 2022 – November 2023

Activity	Month											
	Dec	Jan	Feb	Mar	Apr	May	Jun	Jul	Aug	Sept	Oct	Nov
Create study documents	X											
Create & test REDCap database	X											
Obtain IRB approval		X										
Recruitment			X	X	X	X						
Ongoing data collection			X	X	X	X						
Ongoing qualitative data analysis			X	X	X	X						
Quantitative data analysis							X					
Dissemination (publication)								X	X	X		
Grant writing									X	X	X	X

Appendix Q
Timeline of Study Events with Outcome Measures and Timepoints

BASELINE (Video Call or in person)	Initial & Date completed
Informed Consent documents will be available in English. The consent form will be accessible via REDCap. This visit is to ensure the participant understands the basis of this voluntary study and provides consent to participate in the research study.	
Pre-First Visit (Video Call or in person at 1 st visit)	
We will ask the stroke survivor about their medical history and give the stroke survivor the Montreal Cognitive Assessment (MoCA) or other appropriate cognitive screening test if the participant has aphasia, hemiopsia, and other neurological deficits that cannot be examined using MoCA or a modified MoCA that will assess their cognitive capabilities. We will arrange a time to meet with the stroke survivor and their caregiver on a video call using the computer and this will take only 15 or 20 minutes. We will offer the option to complete the Pre-Intervention Questionnaire of the stroke survivor participant and Burden Scale for Family Caregivers depending on participant and caregiver preferences. This will take 15-20 additional minutes. F	

 1. Assess stroke survivor's medical history 2. Cognition (MoCA) test completed (Appendix J) 	
Inclusion Criteria	

Patients must meet the following criteria for study entry:
 
 • Ischemic, hemorrhagic, or SAH stroke diagnosis within 6 months to 5 years of enrollment. • Dyads will be included if they 
 ◦ Are \geq 18 years old ◦ Can read, write, comprehend ◦ Speak English ◦ Are willing and able to provide informed consent • Caregivers must live in the home with the stroke survivor. 	
Exclusion Criteria	
General	

 • Stroke survivors will be excluded if they do not have score ranges that indicate mild to moderate severity on prior post-stroke neuropsychological tests, or the MoCA (15-25) using normative data based on education, age, and other standard demographic data, or other appropriate cognitive screening test selected by the speech language pathologist (also on this application) if the participant has aphasia, hemiopsia, other neurological or specific cognitive deficits, or demographic factors (e.g., education level) that prevents the participant from being accurately examined using MoCA or a modified MoCA; if cognition is within normal range then a FM (20-50) • Have a history of: 
 ◦ Motion sickness ◦ Vertigo ◦ Dizziness ◦ Seizures (a doctor's note will be requested for participants who do not believe their seizures will be triggered by the VR) ◦ Claustrophobia ◦ Blind/deaf • Cannot hold the controller in their affected arm. 	

	IRB NUM: ER: HSC-SN-22-08 8
	IRB APPROVAL DATE: 03/06/2024

1st Session (Week 1)	Initial & Date completed

3. Pre-Intervention Questionnaire will be given during the first session. (Appendix R)
 
4. Cognition (MoCA or other appropriate) test completed (if not completed during pre-first visit) (Appendix J)
 
5. Fugl-Meyer Upper Extremity Assessment (Appendix K)
 
6. Action Research Arm Test (ARAT) (Appendix L)
 
a. 3,4, and 5 will be completed as a part of standard of care.
 
7. Burden Scale for Family Caregivers – short version will be given to the caregivers of the stroke subjects via REDCap. (Appendix F)
	
 Recruit from stroke units/clinics	
 Study coordinator screens for eligibility requirements	
 Obtain Informed Consent Documents from Dyads	
 Complete the Cognition (MoCA) test (pre-intervention) (Primary Outcome; Appendix J)	
 Complete the Fugl-Meyer Upper Extremity Assessment (pre-intervention) (Primary Outcome; Appendix K)	
 Complete the Action Research Atm Test (ARAT) (pre-intervention) (Primary Outcome; Appendix L)	
 Have the Caregivers complete the Burden Scale for Family Caregivers (Primary Outcome; Appendix F)	
 Arrange sessions schedules with Dyads for the length of the study (2 sessions/week each being an hour minimum in length). Reserve smart room for duration of study.	

 _ Complete the Pre-Intervention Questionnaire (Secondary Outcome; Appendix R) 	

 _ Have the stroke survivor complete the Simulator Sickness Questionnaire (SSQ) at the beginning and end of the first 1-hour session (Primary Outcome; Appendix I) 	
2nd Session (Week 1)	Initial & Date completed

 _ Research Assistant complete the Therapy Follow Up Checklist with Subject before the start of the session. (Secondary Outcome; Appendix M) 	

 _ Have the stroke survivor complete the Simulator Sickness Questionnaire (SSQ) at the beginning and end of the second 1-hour session (Primary Outcome; Appendix I) 	
3rd Session (Week 1)	Initial & Date completed

 Research Assistant complete the Therapy Follow Up Checklist with Subject before the start of the session. (Secondary Outcome; Appendix M) 	

 Have the stroke survivor complete the Simulator Sickness Questionnaire (SSQ) at the beginning and end of the third 1-hour session (Primary Outcome; Appendix I) 	
4th Session (Week 2)	Initial & Date completed

 Research Assistant complete the Therapy Follow Up Checklist with Subject before the start of the session. (Secondary Outcome; Appendix M) 	

 Have the stroke survivor complete the Simulator Sickness Questionnaire (SSQ) at the beginning and end of the fourth 1-hour session (Primary Outcome; Appendix I) 	
5th Session (Week 2)	Initial & Date completed

 Research Assistant complete the Therapy Follow Up Checklist with Subject before the start of the session. (Secondary Outcome; Appendix M) 	

 Have the stroke survivor complete the Simulator Sickness Questionnaire (SSQ) at the beginning and end of the fifth 1-hour session (Primary Outcome; Appendix I) 	
6th Session (Week 2)	Initial & Date completed

 Research Assistant complete the Therapy Follow Up Checklist with Subject before the start of the session. (Secondary Outcome; Appendix M) 	

 Have the stroke survivor complete the Simulator Sickness Questionnaire (SSQ) at the beginning and end of the sixth 1-hour session (Primary Outcome; Appendix I) 	
7th Session (Week 3)	Initial & Date completed

 Research Assistant complete the Therapy Follow Up Checklist with Subject before the start of the session. (Secondary Outcome; Appendix M) 	

 Have the stroke survivor complete the Simulator Sickness Questionnaire (SSQ) at the beginning and end of the seventh 1-hour session (Primary Outcome; Appendix I) 	
8th Session (Week 3)	Initial & Date completed

 Research Assistant complete the Therapy Follow Up Checklist with Subject before the start of the session. (Secondary Outcome; Appendix M) 	

 Have the stroke survivor complete the Simulator Sickness Questionnaire (SSQ) at the beginning and end of the eighth 1-hour session (Primary Outcome; Appendix I) 	

9th Session (Week 3)	Initial & Date completed

 _____ Research Assistant complete the Therapy Follow Up Checklist with Subject before the start of the session. (Secondary Outcome; Appendix M) _____ Have the stroke survivor complete the Simulator Sickness Questionnaire (SSQ) at the beginning and end of the ninth 1-hour session (Primary Outcome; Appendix I) 	
10th Session (Week 4)	Initial & Date completed

 _____ Research Assistant complete the Therapy Follow Up Checklist with Subject before the start of the session. (Secondary Outcome; Appendix M) _____ Have the stroke survivor complete the Simulator Sickness Questionnaire (SSQ) at the beginning and the end of the tenth 1-hour session (Primary Outcome; Appendix I) 	
11th Session (Week 4)	Initial & Date completed

 _____ Research Assistant complete the Therapy Follow Up Checklist with Subject before the start of the session. (Secondary Outcome; Appendix M) _____ Have the stroke survivor complete the Simulator Sickness Questionnaire (SSQ) at the beginning and end of the eleventh 1-hour session (Primary Outcome; Appendix I) 	
Pre-Last Visit (Video Call or in person)	
We will give the stroke survivor the Montreal Cognitive Assessment (MoCA) that will assess their cognitive capabilities. We will arrange a time to meet with them on a video call using the computer and this will take only 15 or 20 minutes.	
1. Cognition (MoCA) test completed (Primary Outcome; Appendix J)	
12th Session (Week 4, last session; in the event that the study participant and/ or caregiver are unable to complete any post-intervention items, we will request a video call to complete any missing items that were not completed on the last session at a time convenient to the stroke participant or caregiver)	Initial & Date completed

 _____ Research Assistant complete the Therapy Follow Up Checklist with Subject before the start of the session. (Secondary Outcome, Appendix M) _____ Have the stroke survivor complete the Simulator Sickness Questionnaire (SSQ) at the beginning and end of the last 1-hour session (Primary Outcome; Appendix I) _____ Complete the System Usability Survey (SUS) via REDCap (Primary Outcome; Appendix G) _____ Complete the Presence Questionnaire (PQ) (Primary Outcome; Appendix H) 	

 Complete the Cognition (MoCA) test (post-intervention, if not completed during the Pre-Last Visit) (Primary Outcome; Appendix J)	
 Complete the Fugl-Meyer Upper Extremity Assessment (post-intervention) (Primary Outcome; Appendix K)	
 Complete the Action Research Atm Test (ARAT) (post-intervention) (Primary Outcome; Appendix L)	
 Complete the Caregiver Burden Questionnaire (Primary Outcome; Appendix F)	
 Complete the Post-Intervention Questionnaire (Participant and Caregiver) (Secondary Outcome; Appendix S)	

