- We believe that this study will generate an estimate of the effect that can be used to inform the development of randomized controlled studies (RCTs).
 - This study will also generate RCTs examining the use of the Oculus VR as a form of stroke rehabilitation that is scalable to the participant's home setting.
 - There are few studies that have examined the role of caregiver engagement on the success of remote stroke rehabilitation.
- The caregiver will be encouraged to use Caregiver Cues (Appendix D) as this will help the caregiver to engage with the participant using encouragement or positive cues to the stroke participants to support them during the session.
- The therapist or RA (who will be trained by the therapist) who is conducting the session will use the Therapist Guided Cues (Appendix E) to guide the stroke participant with problem solving and planning for performing home exercises that will be provided to the participant at the first session.
- The data we obtain from caregivers and stroke survivors (dyads) will inform future studies that examine ways to best support the dyads to improve stroke rehabilitation outcomes and reduce stress in the caregivers. (See Appendix F)

Statistical Analysis

- To address S.A.1., feasibility, usability, and acceptability of the Oculus VR headsets for upper extremity and cognitive therapies will be analyzed as follows: Feasibility: Assessed from the number sessions attended and time spent using the Oculus VR. The minimum number of sessions expected for a user are 2 per week (8 sessions) and the minimum time spent playing Job Simulator is 1 hour per week (4 hours) through the end of the study. Descriptive statistics of the participation rates and measures including frequencies, median and interquartile ranges for sessions attended and time spent using the game. Usability: Descriptive statistics for demographic and clinical data and participant scores on the SUS and PQ will be calculated. (See Appendix G and H) We will refrain from using inferential statistics since this is a pilot study and hypothesis testing is not the objective. Acceptability: Descriptive statistics for scores on the SSQ will be calculated at baseline and after each session (See Appendix I). We will examine the trend of symptoms for each participant.)

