Appendix E

Therapeutic Guided Cues Protocol^{12,13} for the Stroke Survivor Participants to be Used by the Research Assistant .

During the session:

Problem solving:

- What will you gain by doing exercises at today's session?
- (Reinforce with the patient) Flexible coping strategies include:
 - define the problem and goal
 - generate multiple solutions
 - select a solution
 - implement and evaluate

Decision making:

- What will you do if you start to feel dizzy or not well during today's session?

Resource utilization:

- How will you seek assistance from your caregiver today during the session?
- You can ask me to assist you during the session. How will you signal to me that you want to stop?

Partnership with rehabilitation therapist/ RA:

- Do you understand what I am asking you to do?
- Would you like to practice the arm/ hand movements (or using the hand controller) with me before starting the session?

Planning and taking action:

- How will you use the hand controller?
- How will you put the headset on? Who will assist you?
- How many times this week will you come to the AIP apartment for your rehabilitation session?

For arm/ hand exercises at home:

Problem solving:

- What will you gain by doing arm/ hand exercises at home?

Decision making & Planning and taking action:

- Where/ when/ what/ how will you do your arm/ hand exercises?
- How will you know if you are doing your arm/ hand exercises correctly?
- How will you know when to stop doing your hand/ arm exercises?

Resource utilization:

- Can a friend or family member assist you with your arm/ hand exercises?
- Do you have a non-slippery surface at home where you can do your exercises?
- Do you have slip-resistant shoes?

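### Appendix Q books 2 sessions a week (8) but lists 3 a week (12), and the 4-hour play minimum has only session minutes to be judged on

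*Combined protocol and SAP*

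**What the plan says.** **Schedule.** The first-session checklist in Appendix Q reads "Arrange sessions schedules with Dyads for the length of the study (2 sessions/week each being an hour minimum in length". The session list in the same appendix includes "3rd Session (Week 1"), "8th Session (Week 3") and "12th Session (Week 4, last session"). Each of the 12 listed sessions is described as one hour.

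**Feasibility criteria.** The S.A.1 paragraph of the Statistical Analysis section says feasibility is "Assessed from the number sessions attended and time spent using the Oculus VR". It then gives two minima: "The minimum number of sessions expected for a user are 2 per week (8 sessions") and "minimum time spent playing Job Simulator is 1 hour per week (4 hours) through the end of the study". It plans descriptive summaries, including participation rates and the median and interquartile range of sessions attended and of time on the game.

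**Data listed.** For feasibility, Table 1 and Appendix A list the number of sessions attended and the duration of the session in minutes, kept in a staff log. Both tables class these as primary outcomes. Neither lists headset-on or game minutes.

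**The concern.** Two current instructions in one appendix give different numbers of sessions over the same four weeks. Staff who follow the booking line will not fill the 12-session list. The feasibility results and the S.A.2 pre-post scores could then rest on 8 scheduled sessions for some dyads and 12 for others. A participation rate would have no agreed denominator.

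The time criterion is defined on one quantity (play) and the listed data hold another (session length). If the listed field is used, a primary feasibility criterion could be reported as met when actual play fell short of it. These data are meant to inform a later randomised trial, so the dose delivered and the time actually played need to be readable from the report.

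**Working it through.** **Inputs**
- Booked: 2 sessions a week, each at least one hour (Appendix Q, first-session checklist).
- Listed: sessions 1–3 in Week 1, 4–6 in Week 2, 7–9 in Week 3, 10–12 in Week 4, one hour each (Appendix Q).
- Minima: 2 sessions a week (8) and 1 hour of play a week (4 hours) (Statistical Analysis, S.A.1).
- Time field: session minutes only (Table 1; Appendix A).

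**The plan's own figures**
- 2 × 4 weeks = 8 sessions and 1 × 4 weeks = 4 hours. Both stated minima reproduce.

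**Schedule**
- Booking line: 2 × 4 = 8 sessions, or 8 session-hours at one hour each.
- Session list: 3 × 4 = 12 sessions, or 12 session-hours.
- Ratio: 12/8 = 1.5. At two sessions a week the 8th would fall in Week 4; the list puts it in Week 3.
- A survivor attending 8 sessions has a rate of 8/8 = 100% on the booking line and 8/12 = 67% on the list.

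The choice also changes how hard the 8-session minimum is to meet. If 8 are booked, none can be missed unless it is rebooked; if 12 are offered, four can be. As an illustration only, assume independent attendance at each session with the same probability and no rebooking:

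| Assumed attendance per session | Reach 8 of 8 booked | Reach at least 8 of 12 listed |
|---|---|---|
| 0.7 | 0.058 | 0.724 |
| 0.8 | 0.168 | 0.927 |
| 0.9 | 0.430 | 0.996 |

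The documents give no attendance rate, so these rows show direction and are not a forecast.

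**Time**
- Floor: 4 h × 60 = 240 play minutes.
- Eight one-hour sessions: 8 × 60 = 480 session minutes, and 480/240 = 2.0 times the floor. Twelve: 12 × 60 = 720, and 720/240 = 3.0 times.
- Average play per session needed to reach the floor: 240/8 = 30 minutes over 8 sessions; 240/12 = 20 minutes over 12.

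So anyone who meets the session minimum with one-hour sessions passes the time minimum automatically on the listed field. Play averaging below 30 minutes (8 sessions) or 20 minutes (12 sessions) would not show.

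**Are session and play minutes the same thing?** Not by the plan's description. Breaks are encouraged every 20 minutes (Potential Problems and Alternative Approaches). The sickness questionnaire is completed at the start and end of each session, and the first and last sessions also list assessments (Appendix Q). The documents do not say how many minutes of a session are play.

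**The case against.** **Schedule.** The strongest reply is that 2 a week is the floor from the analysis section carried into the checklist, with the 12 dated entries as the full schedule and only the words for at least left out. That is probably what was meant, and staff facing 12 numbered sign-off blocks may notice. As written, though, the word for minimum in the booking line attaches to the hour, and the line is an instruction to schedule. A reader might also infer that the analysis section's 8 contradicts the 12-session list. It does not, because 8 is stated there as a minimum.

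**Dose.** A reader might infer that the dose behind the S.A.2 scores will be unknown. It will not: sessions attended are logged for every survivor. What is unclear is how many were meant to be offered. Nor does the Appendix E cue "How many times this week will you come to the AIP apartment for your rehabilitation session" show that weekly dose is left to the dyad. It sits among planning prompts in a coaching script and sets no schedule.

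**Time.** The analysis section names the right quantity, and the table entry may be shorthand. Some wording suggests that a session largely means the VR period: the therapy checklist is done before the session starts, and Data Management refers to gaming sessions. This narrows the likely gap but does not define the field. Camera recordings might allow play time to be recovered, but their stated purpose is therapist review of progress, and no derivation of play time is described.

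It is tempting to add that four one-hour visits would satisfy the 4-hour figure on session minutes (4 × 60 = 240). That survivor would already fail the companion 8-session minimum, so the example does not show a poor attender passing feasibility overall. For someone who attends 8 sessions, play must fall below half of each hour before the result changes, and brief breaks alone would be unlikely to do that.

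**Conclusion.** Both points hold and are worth fixing; the consequence is modest. Appendix Q contradicts itself, 8 sessions against 12 over four weeks, and the attendance floor of 8 does not resolve it. The 4-hour play minimum cannot be judged on the field that Table 1 and Appendix A list. With one-hour sessions and at least 8 attended, it is always met on that field.

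This rests on the four-week course and one-hour sessions in Appendix Q, and on session duration meaning the whole visit. If the team already logs headset time under that name, the second point reduces to a label. How often a survivor's result would change cannot be estimated, because play minutes per session are not given.

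A reader might infer that a trial conclusion or the sample size is in doubt. The documents do not support that: S.A.1 is descriptive, and no success rule or go/no-go decision is tied to either minimum. What is affected is the dose delivered and how feasibility is reported.

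**What to change.** 1. In the Appendix Q booking line, change 2 sessions a week to 3, to match the 12-session list. Keep 8 as the attendance minimum in the analysis section.
2. Add game or headset-on minutes per session to the existing staff log, name that field in Table 1 and Appendix A, and judge the 4-hour minimum on it alone.
3. For survivors already treated, take play time from the session recordings if they were kept. Where it cannot be recovered, report session minutes under that name and do not score them against the 4-hour minimum.
4. Divide any attendance rate by the number of sessions scheduled for that dyad, and report that number.

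The cost is one corrected line, one extra log column and two table entries, plus staff time to read play minutes from any recordings used. Feasibility figures may look slightly less favourable.
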